11.6 Modification of Study Protocol

After the protocol is approved by the Ethics Committee, if the protocol is amended during the implementation process, such amendment should be implemented with the approval from the Ethics Committee.

Any amendments to the protocol, major or non-major protocol amendments, are required to be made in writing. Substantial protocol amendments that definitely affect the safety of subjects, the scope of the study, or the scientific quality of the study should be approved by the Ethics

Committees of all sites. In order to protect the safety of all subjects in the study, the above requirements should not prevent the investigator or Sponsor from taking any urgent measures. If the investigator believes that the protocol must be amended immediately for safety reasons, the investigator should notify the Sponsor's designated institution in a timely manner, and inform the Ethics Committee of the study site in accordance with the policies formulated by the Ethics Committee that approved the study, local regulations and policies. Any changes that only affect the study management do not require substantial protocol amendments or approval from the Ethics Committee, but these changes must be notified to the Ethics Committee. In these cases, the Sponsor will send an official letter to the Ethics Committee detailing the changes.

Protocol No.: HTD1801.PCT103

11.7 Protocol Deviation

The investigators should carry out this clinical study according to the clinical study protocol approved by the Ethics Committee and in accordance with GCPs. The protocol is established to enable investigators to comply with Section 4, ICH E6. During the study, the investigator should not deviate from the protocol unless urgent measures are taken to eliminate the direct harm to the subjects. In the event of other unexpected circumstances that require deviation from the procedures specified in the protocol, the investigator should consult with the medical monitor (and the Ethics Committee, if necessary) to determine appropriate measures.

The study site should record all protocol deviations, including but not limited to, the time of the protocol deviation, the time of discovery, the description of the event and the measures taken. In case of serious protocol deviation, the study site should promptly notify the medical monitor, CRA, and Ethics Committee.

11.8 Case Report Form

The CRO database programmer will create an eCRF on the EDC system, and in eCRF, only appropriate identification codes (such as site number and subject number) and initials are used to identify different subjects. eCRF is used to record the clinical study data of subjects and is an integral part of the study and related study reports. Therefore, the input must be accurate and complete. eCRF is maintained in the EDC system by the investigator or the investigator-authorized staff (indicated in the study authorization form). All data input must be completed and stored. The investigator must declare the authenticity of all information in the eCRF through an electronic signature.

During the clinical study, eCRF must be completed after each visit to record subjects' conditions.

Medical history records and other records related to subjects' disease progression during the study are kept by the investigator. These records should contain: original or photocopy of laboratory data and other medical test results (such as ECG). These data must be kept in the study site together with subjects' medical records.

11.9 Monitoring

The Sponsor or the CRO entrusted by the Sponsor shall conduct the monitoring.

Before a site is selected for the study, a site selection visit will be conducted to confirm that the site, equipment, and staff meet the requirements of the protocol and GCP.

During the study, on-site monitoring at the study site is carried out by the monitor at regular intervals. For each monitoring, the date of the visit should be recorded in the Visit Record Form of the study site. The site monitoring will be accepted by the Sponsor depending on the study quality.

The study monitoring activities by the monitor include:

 The monitor should initiate the visits at the study site, collect and distribute necessary prestudy documents; give instructions to the investigators and site staff on the protocol, study procedures and expectations; obtaining assurances that investigators will conduct the study in accordance with study requirements and GCPs, and introducing study materials to investigators and corresponding study staff.

Protocol No.: HTD1801.PCT103

• Monitoring visits: As required by the GCP, monitors participating in the current study should be fully informed about confidentiality issues and compare data in the eCRF with data from hospital or clinical records (raw data). Before the study, the monitor should discuss with the investigator the specific items required as raw data, determine the nature and location of all raw data, and ensure that the Sponsor or investigator is aware of the source of the raw data used to complete the eCRF, and the inspection and verification authorities of the monitor authorized by the Sponsor; all observations and findings during the monitoring process must be verifiable. If electronic records are kept in the Study Institution, the verification method must be discussed with the study member.

Raw data must be available to demonstrate at least:

- Subject identity, eligibility and participation in the study;
- Appropriate informed consent procedures;
- Date of visit;
- Records of safety and efficacy parameters;
- Adequate reporting and visits of AEs;
- Concomitant medications and treatment;
- Drug receipt/dispensation/return records;
- Information on administration of the investigational drug;
- Subject's completion of treatment, discontinuation of treatment, or withdrawal from the study, with appropriate reasons;
- The data is true, accurate and complete;
- The safety and rights of subjects are protected;
- Investigator implementation complies with currently approved protocol, GCPs and all relevant regulatory requirements.

The objectives of monitoring include:

- Check and evaluate study schedule;
- Review the study data collected;
- Implement the source document verification process;
- Identify any problems and develop solutions.

During the study, the monitor should have direct access to all relevant documents with the consent of the investigators, and the investigators should ensure that they and the relevant investigator will meet the monitor regularly to discuss the findings of the visit and any related issues.

11.10 Intellectual Property

All information obtained from the Sponsor is regarded as the Sponsor's intellectual property. Therefore, investigators and all other relevant personnel must keep the information confidential and shall not disclose it to a third party without the Sponsor's prior consent.

Protocol No.: HTD1801.PCT103

11.11 Subjects' Privacy

Investigators must maintain the privacy of subjects. In all the documents submitted to the Sponsor, only the screening number/randomization number and initials of subjects can be used to identity them, and their names should not be indicated. Investigators must keep the private information such as names and addresses of subjects strictly confidential and cannot submit them to the Sponsor.

12. PUBLICATIONS

The ownership of the study results remains with the Sponsor. The investigators should guarantee not to publish or release any content related to the study and/or study results by journal publications, academic or commercial conferences without the written permission of the Sponsor. Regarding the manuscript and publication, the Sponsor makes the final decision. In addition, the investigators should be aware that the Sponsor will not withhold permission to publish without reason after communication.

Protocol No.: HTD1801.PCT103

To prevent inadvertent disclosure of confidential information or unprotected inventions, the investigators must notify the Sponsor in advance, consult with, or review any planned publications or release in other form (publication/release forms include, but are not limited to, journal articles, posters, guest lecture, etc.). The Sponsor may require the investigators to delete any previously unpublished confidential information prior to publications.

13. DATA STORAGE

13.1 Source Data and Source Documents

In this study, the source data includes records of clinical findings, observations, and other related activities for reconstruction and evaluation of the study. The raw data is contained in the source documents.

Protocol No.: HTD1801.PCT103

The source documents involved in the study are original records, documents and data (such as hospital medical records, medical images, laboratory records, memos, subject diaries or evaluation forms, drug dispensing records, automatically recorded data from instruments, microfilm, photographic plates, X-rays, subject's documents, and study-related documents and records kept by pharmacies, laboratories, and medical technology departments, including certified copies, ect.). The source documents must be retained to support the information provided in the eCRF.

13.2 Data Storage in Study Sites

13.1.1 Data related to the Ethics Committee

The personnel responsible for data storage in the study site must keep the minutes and abstracts of the Ethics Committee meetings until 5 years after the study is suspended or completed. If the Sponsor wishes to keep it for a longer period of time, both parties will discuss and decide on the storage time and method. The personnel responsible for data storage or the investigator needs to contact the Sponsor if any changes made by the study site to the data storage.

13.1.2 Data related to the implementation of the study

The personnel responsible for data storage in the study site must keep the following documents until 5 years after the investigational drug is approved for marketing. If the Sponsor wishes to keep it for a longer period of time, both parties will discuss and decide on the storage time and method. The personnel responsible for data storage or the investigator needs to contact the Sponsor if any changes made by the study site to the data storage.

- Raw data
- Original or copy of the study contract, ICFs, and other GCP-related materials provided by the study site staff;
- Study protocol, GCP-related materials from the Ethics Committee, or GCP-related materials from other sources:
- Records of investigational drug management and other records related to study implementation.

13.3 Data Storage by The Sponsor

The Sponsor will keep the following materials (including documents and data) until 5 years after the investigational drug is approved for marketing. According to relevant regulations, a longer storage time may be required. It is the Sponsor's responsibility to inform the investigator/study site of when the data is no longer necessary to be kept.

- The original or copy of study protocol, study contract, and study report, or GCP-related materials provided by the Sponsor;
- Case report form, GCP-related notice, or GCP-related materials from the investigator;
- Records of monitoring and audit, or other related operation records;

Nomenclature HTD1801/Clinical Phase II

Protocol No.: HTD1801.PCT103

- Data obtained during the study;
- Relevant records required by GCP.

APPENDIX 1: Hepatoprotective Drugs

Hepatoprotective drugs commonly used in clinical practices include but are not limited to the following:

Protocol No.: HTD1801.PCT103

Туре	Drug Name	
Hepatocyte Membrane Repair and Protective Agents	Hepatocyte growth-stimulating hormone, polyene phosphatidylcholine, etc.	
Alexipharmacons	Glutathione, N-acetylcysteine, tiopronin, penicillamine, etc.	
Enzyme-lowering Hepatoprotective Drugs	Bifendatatum, bicyclol, etc.	
Choleretic Drugs	Ademetionine, ursodeoxycholic acid, anethole trithione, etc.	
Hepatoprotective Drugs Promoting Energy Metabolism	Water-soluble vitamins (such as vitamin C, vitamin B complex), coenzyme A, coenzyme Q10, inosine, ornithine aspartate, alprostadil, etc.	
Chinese Herbal Medicines and Extracts	Glycyrrhizin acid preparations, silymarin, oxymatrine, etc.	

The above drug list is for reference only, and investigators can make their own judgments according to the actual situation.

APPENDIX 2: Chemical Drugs, Traditional Chinese Medicines or Dietary Supplements for Weight Loss

Non-hyperglycemic weight loss drugs, health care products and foods commonly used in clinical practices include but are not limited to the following:

Protocol No.: HTD1801.PCT103

Туре	Drug Name
Lipase Inhibitors	Orlistat, etc.
Amylase Inhibitors	White kidney bean extract, etc.
Appetite Suppressants	Fenfluramine, sibutramine, etc.
Chinese Herbal Medicines	Lipid-lowering weight loss tablets, light-weight weight loss tablets, lipid-lowering weight loss capsules, etc.

The above drug list is for reference only, and investigators can make their own judgments according to the actual situation.

APPENDIX 3: List of Bacteria Used in Food

According to the List of Bacteria Used in Food promulgated by the Ministry of Health P.R.China, bacteria that may meet the definition of "probiotics" are mainly from *Lactobacillus* and *Bifidobacterium*, and may also be *Bacillus*, *Enterococcus*, *Streptococcus*, *Pediococcus*, *Leuconostoc*, *Clostridium butyricum*, *Actinomycetes* and *Saccharomyces*, etc. The list below is for reference only, and investigators can make their own judgments based on the actual situation.

Protocol No.: HTD1801.PCT103

	Name in Latin
I	Bifidobacterium
1	Bifidobacterium adolescentis
2	Bifidobacterium animalis (Bifidobacterium lactis)
3	Bifidobacterium bifidum
4	Bifidobacterium breve
5	Bifidobacterium infantis
6	Bifidobacterium longum
II	Lactobacillus
1	Lactobacillus acidophilus
2	Lactobacillus casei
3	Lactobacillus crispatus
4	Lactobacillus delbrueckii subsp. Bulgaricus (Lactobacillus bulgaricus)
5	Lactobacillus delbrueckii subsp. lactis
6	Lactobacillus fermentium
7	Lactobacillus gasseri
8	Lactobacillus helveticus
9	Lactobacillus johnsonii
10	Lactobacillus paracasei
11	Lactobacillus plantarum
12	Lactobacillus reuteri
13	Lactobacillus rhamnosus
14	Lactobacillus salivarius
III	Streptococcus
1	Streptococcus thermophilus

APPENDIX 4: Lipid-Controlling Drugs

Lipid-controlling drugs commonly used in clinical practices include but are not limited to the following:

Protocol No.: HTD1801.PCT103

	Туре	Drug Name
Cholesterol Lowering Drugs	Statins	Lovastatin, simvastatin, pravastatin, fluvastatin, atorvastatin, rosuvastatin and pitavastatin, xuezhikang capsules, etc.
	Cholesterol absorption inhibitors	Ezetimibe
	Probucol	
	Bile acid sequestrants	Cholestyramine, colesevelam
	Other lipid-lowering drugs	Zhibitai capsules, policosanol
TG Lowering Drugs Fibrates		Fenofibrate tablets, micronized fenofibrate, gemfibrozil, bezafibrate
	Niacin	Niacin (vitamin B3)
	High-purity fish oil drug products	
Novel Lipid-lowering Drugs	Microsomal TG transfer protein inhibitors	Lomitapide
	Apolipoprotein B ₁₀₀ synthesis inhibitors	Mipomersen
	Proprotein convertase subtilisin 9\kexin9 inhibitors	Evolocumab, alirocumab

The above drug list is for reference only, and investigators can make their own judgments according to the actual situation.

APPENDIX 5: Calculation Formula

Calculation Formula for Glomerular Filtration Rate (GFR)

GFR is calculated using the CKD-EPI formula:

Serum creatinine unit conversion: 1 mg/dL = $88.4 \mu mol/L$

Gender	Scr Range	EPI-GFR Formula, unit: mL·min ⁻¹ · (1.73 m ²) ⁻¹
		EPI-GFR= $144 \times [Scr(mg/dL) / 0.7)]^{-0.329} \times 0.993^{age}$
	Scr > 0.7mg/dL	EPI-GFR= $144 \times [Scr(mg/dL) / 0.7)]^{-1.209} \times 0.993^{age}$
Male	$Scr \leq 0.9 mg/dL$	EPI-GFR= $141 \times [Scr(mg/dL) / 0.9)]^{-0.411} \times 0.993^{age}$
	Scr > 0.9mg/dL	EPI-GFR=141×[Scr(mg/dL) / 0.9)] ^{-1.209} ×0.993 ^{age}

Protocol No.: HTD1801.PCT103

QTcF Calculation Formula

QTcF=QT/RR^{0.33} (RR is the normalized heart rate)

APPENDIX 6: Birth Control, Definition of Female Subjects of Childbearing Age, and Contraception Requirements

Protocol No.: HTD1801.PCT103

> Definition of Female Subjects of Childbearing Age

Female subjects of non-childbearing age are defined as postmenopausal female subjects and premenopausal female subjects who had undergone sterilization. Postmenopause is defined as the absence of menstrual periods for ≥12 consecutive months without alternative medical measures. FSH >40 MlU/mL can be determined as menopause by follicle-stimulating hormone (FSH) test in uncertain subjects. Sterilization procedures include bilateral tubal ligation or bilateral oophorectomy or hysterectomy.

Female subjects of childbearing age are defined as women who are anatomically and physiologically able to get pregnant without sterilization from menarche to menopause.

> Contraception Requirements

Female subjects of childbearing age must be negative in the pregnancy test at the screening phase;

During the screening phase to the last dose, female subjects of childbearing age and male subjects must also agree to one of the following operations:

- Complete abstinence of sex activities. Periodic abstinence (e.g., calendar, ovulation, symptom-temperature, postovulation method) is not permitted.
- One of the contraceptive methods with <1% correct failure rate:
 - Intrauterine device (IUD) or intrauterine hormone-releasing systems with an annual failure rate < 1%
 - Vasectomy for male subjects;
 - Double-barrier method of contraception: condom and/or occlusive cap (diaphragm or cervical cap/dome cap), a barrier method with spermicide (foam/gel/film/cream/suppository) must be used as a supplementary measure.

The following contraception methods can be accepted within 3 months after the last dose:

- Rational use of combined (estrogen and progestin-containing) oral/injectable/transdermal hormonal contraceptives that inhibit ovulation;
- Rational use of oral/injectable/transdermal hormonal contraceptives that only contain estrogen and progestin and inhibit ovulation.

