- 10. Pregnancy test: for female subjects of childbearing age only (see APPENDIX 6). The blood pregnancy test is required at V1, V3, and V7 in the local laboratory. During the study V5 and V6, a urine pregnancy test should be performed in local laboratories, and if the urine pregnancy test is positive, a blood pregnancy test should be performed immediately to exclude or verify the pregnancy. If the blood pregnancy test at V1 is positive, the subject will not be able to participate in the study. Female subjects should withdraw from the study immediately once the blood pregnancy test is positive.
- 11. Thyroid function tests: free tri-iodothyronine (FT3), free thyroxine (FT4) and thyroid stimulating hormone (TSH).
- 12. Evaluation endpoints: for the sample collection time window, see APPENDIX 8.
- 13. Except for the blood samples collected after meals, other blood samples should be collected under the fasting condition (V1, V3, V4-7, withdrawal visit, pre-salvage therapy visit, and salvage therapy evaluation visit). It is recommended to collect the fasting blood samples at 7:00 ~ 10:00 a.m.
- 14. After meals: standard meals are given. For detailed procedures, please refer to APPENDIX 9. For the time window, please refer to the APPENDIX 8.
- 15. Liver function and blood lipid test: for LDL-C, HDL-C, TG, TC, AST, ALT, GGT, TBIL, the time windows are shown in APPENDIX 8.
- 16. Feces collection (if any): feces samples of subjects should be collected from the day before the visit to the day of the visit according to the subject's own conditions if possible. Refer to the *Laboratory Operation Manual* for the relevant procedures of feces collection. A lifestyle background survey can be conducted at the same time as the baseline feces collection to better guide the subject's lifestyle.
- 17. PPK blood sample collection: V4 blood samples should be collected under the fasting condition in the forenoon, V5-V7 blood samples should be collected before breakfast on the same day (before the first administration) (time window: within 1 hour before dosing).
- 18. 12-lead ECG: subjects should be checked in the supine position after rest, and the heart rate, PR interval, QT interval, RR interval, QTcF (see APPENDIX 5 for calculation formula) and QRS complex duration should be recorded.

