TREATMENT (GUIDELINES FOR THE PREVENTION AND TREATMENT OF		96
1 YPE 2 DIABETES MELLITUS IN CHINA (2020))98	TYPE 2 DIABETES MELLITUS IN CHINA (2020))	98

LIST OF ABBREVIATIONS

Protocol No.: HTD1801.PCT103

Abbreviation	Full Name in English
AE	Adverse event
ALP	Alkaline phosphatase
ALT	Alanine aminotransferase
AST	Aspartate aminotransferase
AUC _{0-t}	Area under the curve from pre-dose to the time of the last observation
BBR	Berberine
-	
BBR·Cl	Berberine hydrochloride
BID	Twice a day
BMI	Body mass index
CAP	Controlled attenuation parameter
CDE	Center for drug evaluation, national medical products administration
C _{max}	Maximum plasma concentration
CRO	Contract research organization
CTCAE	Common terminology criteria for adverse events
CYP450	Cytochrome P450
DBIL	Direct bilirubin
DPP-4	Dipeptidyl peptidase IV
eCRF	Electronic case report form
eGFR	Estimated glomerular filtration rate
EDC	Electronic data capture
FAS	Full analysis set
FDA	Food and drug administration
FPG	Fasting plasma glucose
FXR	Farnesoid X receptor
G6PD	Glucose-6-phosphate dehydrogenase
GCP	Good clinical practice
GGT	Gamma-Glutamyl Transferase
GLP-1	Glucagon-like peptide-1
HbA1c	Glycosylated hemoglobin
HBsAg	Hepatitis B virus surface antigen
HCV-Ab	Hepatitis C virus antibody
HDL-C	High-density lipoprotein cholesterol
HED	Human equivalent dose
HIV-Ab	Human immunodeficiency virus antibody
IC ₅₀	50% inhibitory concentration
ICF	Informed consent form
ICH	International council for harmonisation of technical requirements for
	pharmaceuticals for human use
IR	Insulin resistance
ITT	Intention-to-treat analysis
LDL-C	Low-density lipoprotein cholesterol
LLN	Lower limit of normal
LOCF	Last observation carried forward

Abbreviation	Full Name in English
LSM	Liver stiffness measurement
MedDRA	Medical dictionary for regulatory activities
MMRM	Mixed model repeated measures
MTD	Maximum tolerated dose
NASH	Nonalcoholic steatohepatitis
NOAEL	No observed adverse effect level
NYHA	New york heart association
PKS	Pharmacokinetic set
PPK	Population pharmacokinetics
PPS	Per protocol set
PSC	Primary sclerosing cholangitis
PT	Preferred terms
QA	Quality assurance
QTcF	Corrected QT interval by Fredericia's formula
SAE	Serious adverse event
SGLT2i	Sodium-glucose cotransporter-2 inhibitor
SOC	System organ class
SS	Safety set
SOP	Standard operation procedure
SUSAR	Suspected unexpected serious adverse reaction
SMBG	Self-monitoring of blood glucose
T2DM	Type 2 diabetes mellitus
TBIL	Total bilirubin
TC	Total cholesterol

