- 23. Subjects who have suffered from severe infection (such as acute pancreatitis, COVID-19) or severe trauma, or have undergone major surgery within 3 months prior to screening and are judged to be inappropriate to participate in this study by the investigator.
- 24. Subjects who have the history of the following acute or chronic liver diseases at screening (V1): autoimmune hepatitis, primary biliary cholangitis, alcoholic liver disease, hepatolenticular degeneration, or drug-induced liver injury.
- 25. Subjects who have the history of malignant tumors within 5 years prior to screening (except for cured basal cell carcinoma of the skin, carcinoma cervix in situ), or being assessed for potential malignant tumors at screening (V1).
- 26. Subjects who have the history of psychiatric diseases or are receiving drug treatment, and are judged to be inappropriate to participate in this study by the investigator at screening (V1).
- 27. Subjects who have had the following history within 12 months prior to screening: Decompensated heart failure (New York Heart Association [NYHA] Class III or IV), unstable angina, myocardial infarction, percutaneous coronary intervention, coronary bypass transplantation, hemorrhagic stroke, and ischemic stroke (except lacunar infarction).
- 28. Subjects who have clinically significant abnormalities in 12-lead ECG and require treatment or close follow-up (such as Grade II or III atrioventricular block, atrial fibrillation, atrial flutter, pre-excitation syndrome, etc.) at screening (V1); or QT interval corrected by Fridericia formula (QTcF) > 470 ms (male) or QTcF > 480 ms (female) (see APPENDIX 5 for the calculation formula) at screening.
- 29. Etiological test at screening (V1): positive for hepatitis B surface antigen and hepatitis B viral load (HBV-DNA) above the lower limit of detection of the local laboratory; or positive for anti-hepatitis C antibody and hepatitis C viral load (HCV-RNA) above the lower limit of detection of the local laboratory; or positive for treponema pallidum antibody (TP-Ab); or positive for human immunodeficiency virus antibody (HIV-Ab).
- 30. Subjects whose laboratory parameters are within any of the following ranges at screening (V1):
 - ALT \geq 5×ULN, AST \geq 5×ULN;
 - ALP $> 2 \times$ ULN:
 - DBIL> 1.5× ULN;
 - TBIL> 1.5× ULN;
 - Serum TG \geq 4.52 mmol/L (400 mg/dL), or serum LDL-C \geq 5.69 mmol/L (220 mg/dL);
 - Hemoglobin <1 ×LLN;

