7.3.2 Vital signs

Pulse, temperature, sitting blood pressure (systolic and diastolic) measurement. Subjects should be measured at rest. It is recommended that blood pressure be measured on the same arm for each subject at each visit throughout the study.

Protocol No.: HTD1801.PCT103

7.3.3 12-lead ECG

The subject should receive the 12-lead ECG in the supine position after rest. The heart rate, PR interval, QT interval, RR interval, QTcF (see APPENDIX 5 for calculation formula) and QRS complex duration should be recorded. In the event of an abnormal ECG during the visit, the investigator and/or authorized investigator may decide whether to repeat the test based on the subject's clinical condition and evaluate the test results. An unscheduled visit for a 12-lead ECG may also be arranged if clinically indicated.

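### Appendix 5 defines RR in the QTcF formula as the normalized heart rate, with no unit or conversion; read literally this reverses the rate correction, so the definition should be reworded to the RR interval in seconds.

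*Protocol*

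**What the plan says.** Appendix 5 (Calculation Formula) prints QTcF = QT/RR^0.33 and adds that "RR is the normalized heart rate". It does not say how the rate is normalized and gives no unit.

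Four places rely on that appendix:

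- Exclusion criterion 28, in the synopsis and in Section 3.2, excludes at screening a subject with "QT interval corrected by Fridericia formula (QTcF) > 470 ms (male) or QTcF > 480 ms (female" and refers to Appendix 5 for the formula.
- Note 18 to the study process table and Section 7.3.3 both require "heart rate, PR interval, QT interval, RR interval, QTcF" to be recorded, and both refer to Appendix 5 for QTcF.

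The method is named as Fridericia in criterion 28 and, with a variant spelling, in the list of abbreviations ("Corrected QT interval by Fredericia's formula"). Section 10.4.5 analyses the ECG by reference to the laboratory rule, that is, as visit values and changes from baseline. No other place in the protocol defines RR in the formula.

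**The concern.** A rate correction exists because QT shortens as the heart speeds up. Dividing by the RR interval in seconds, which is below 1 when the rate exceeds 60 bpm, raises the corrected value as it should. A normalized heart rate, read in its most direct sense as HR/60, is the reciprocal of that interval. Dividing by it lowers QTcF further at fast rates and raises it at slow ones.

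The protocol's own ECG list treats heart rate and RR interval as different quantities, so the appendix gives the symbol RR a meaning that conflicts with the recorded variables. Appendix 5 is the only calculation rule given for an eligibility limit and for a safety variable.

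If a site followed the parenthesis, a subject above the 470 or 480 ms limit with a heart rate above 60 bpm could be admitted, a subject with a slow heart rate could be excluded wrongly, and a change in heart rate on treatment would appear as a change in QTcF.

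**Working it through.** The protocol states no numerical QTcF result, so there is no figure to reproduce. The check evaluates the printed formula under two definitions of RR.

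**From the protocol:** QTcF = QT/RR^0.33 (Appendix 5); limits of 470 ms for men and 480 ms for women (criterion 28).

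**Assumed for illustration, not in the protocol:** the QT values and heart rates below.

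**Definitions compared:**
- Interval: RR = 60/HR, in seconds.
- Literal: RR = HR/60.

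**Ratio of literal to interval value:**

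[QT/(HR/60)^0.33] / [QT/(60/HR)^0.33] = (60/HR)^0.66

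- 50 bpm: 1.2^0.66 = 1.128, or +13%
- 60 bpm: 1, no difference
- 75 bpm: 0.8^0.66 = 0.863, or -14%
- 90 bpm: 0.667^0.66 = 0.765, or -24%

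**QTcF for QT 400 ms:**

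| HR (bpm) | RR = 60/HR | RR = HR/60 |
|---|---|---|
| 50 | 376.6 | 424.8 |
| 60 | 400.0 | 400.0 |
| 75 | 430.6 | 371.6 |
| 90 | 457.3 | 349.9 |
| 100 | 473.4 | 337.9 |

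**Effect on criterion 28.** For QT 415 ms at 90 bpm:
- Interval: 415/0.667^0.33 = 474.4 ms, above 470, so a man is excluded.
- Literal: 415/1.5^0.33 = 363.0 ms, so he is not.

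This pair was chosen to sit just above the limit. A view that does not depend on one chosen QT is the QT at which the 470 ms limit is reached:
- At 90 bpm: 470 × 0.667^0.33 = 411 ms by interval, against 470 × 1.5^0.33 = 537 ms literally.
- At 50 bpm: 499 ms by interval, against 443 ms literally.

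The literal reading therefore loosens the criterion at fast rates and tightens it at slow ones.

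**Effect on change from baseline.** Hold the interval-based QTcF at 420 ms. Under the literal reading the value is 420 × 0.8^0.66 = 362.5 ms at 75 bpm and 420 × 0.75^0.66 = 347.4 ms at 80 bpm. A rise of 5 bpm shows as a fall of about 15 ms with no change in corrected QT.

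**Exponent.** Using 1/3 in place of 0.33 moves the interval-based values for QT 400 ms by less than 1 ms. The exponent is not the problem.

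**The case against.** The strongest defence is that the formula itself is right and only its gloss is loose. The protocol does not say how the rate is normalized. If 60/HR was meant, that is the RR interval in seconds and nothing is wrong with the arithmetic; a translation slip is plausible. The symbol RR, the named Fridericia method and the requirement to record an item called RR interval all point a careful reader to the correct input. To make the error, a site would have to pass over that recorded value and construct an undefined one.

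Nor does the protocol say that QTcF is calculated by hand. Note 18 and Section 7.3.3 say only that it should be recorded, and an ECG device may supply it. Criterion 28 also separately excludes clinically significant ECG abnormalities that need treatment or close follow-up, which is a partial second check. Because QT and RR interval are both recorded, on-treatment QTcF can be recomputed at analysis. The HbA1c analysis and the sample size are untouched.

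Most of this stands, and it limits the consequence. It does not make the parenthesis right: the benign reading needs a reciprocal that is not printed, and the more direct reading gives the reversed correction. Re-derivation can repair the safety summaries, but it cannot undo an eligibility decision already taken at screening.

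**Conclusion.** The definition of RR in Appendix 5 is wrong as worded and conflicts with the protocol's own list of ECG variables. Under the literal HR/60 reading the rate correction is reversed, by a factor of (60/HR)^0.66: about -14% at 75 bpm and -24% at 90 bpm, with the opposite sign below 60 bpm. That is large enough to flip the 470 ms exclusion in the illustrative case.

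The size rests on two conditions: that normalized means HR/60, and that QTcF is computed from the printed definition rather than taken from a device or from the recorded RR interval. The individual QT and heart-rate examples are assumptions.

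A reader might infer that subjects above the limits will be admitted and that real prolongation on treatment will be hidden. The documents do not support that, because they do not say how sites obtain QTcF and they record the quantities needed to recompute it. A reader might also infer that the formula is wrong; its form and exponent are sound. This is a correction of a definition that should be made, and it does not bear on the primary analysis.

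**What to change.** In Appendix 5, replace the parenthesis after the QTcF formula with: *(RR is the RR interval in seconds, i.e. 60 / heart rate in beats per minute)*. This matches an item that Section 7.3.3 and note 18 already require, and it leaves the formula, the limits in criterion 28 and the ECG schedule unchanged. The cost is one line in an appendix. Central derivation of QTcF is not needed to cure the defect and would be a separate operational change.
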